**4.7.2.2.3. Open-Label vs. Double-Blind Placebo-Controlled Period****MVIC**

The effect of ACE-083 administered during the open-label extension compared to the treatment administered in the double-blind placebo-controlled phase will be examined for those receiving ACE-083 during the double-blind phase and separately for those receiving placebo during the double-blind phase by comparing the average absolute and/or percent changes [depending on the parameter] observed between Day 190 and pre-first treatment baseline (1st 6 months) and Day 358 versus Day 190 (2nd 6 months) using an ANCOVA model.

Possible covariates to be included into the model are SEQUENCE, MRC-MMT SCORE, CMT-TYPE and BASELINE where:

- SEQUENCE represents the treatment sequence from double blind to open-label (ACE-083 → ACE-083 or Placebo → ACE-083)
- MRC-MMT SCORE represents the conversion of the screening MRC-MMT grade to the decimal version as follows: 5 = 5.0, 5- = 4.67, 4+ = 4.33, 4 = 4.0, 4- = 3.67, 3+ = 3.33, 3 = 3.0, 3- = 2.67, 2+ = 2.33, 2 = 2.0, 2- = 1.67, 1+ = 1.33, 1 = 1.0
- CMT TYPE refers to the type of CMT (e.g. CMT1 or CMTX)
- BASELINE represents the baseline value from the double-blind phase

Least squares estimates of the SEQUENCE effect and 90% confidence intervals will be provided.

If the Day 358 and/or Day 190 assessments have no missing data, then the above ANCOVA model will be used for analysis. If missing data is present, a standard multiple imputation with the above ANCOVA model will be used for analysis as described in [Section 4.11.1](#).

In addition, a line graph of the mean ± SEM of the percent change from baseline will be provided by sequence for each scheduled time.

Additional analyses may be performed as appropriate.

### **MRC-MMT Decimal Score**

The effect of ACE-083 administered during the open-label extension compared to the treatment administered in the double-blind placebo-controlled phase will be examined for those receiving ACE-083 during the double-blind phase and separately for those receiving placebo during the double-blind phase by comparing the average absolute change [depending on the parameter] observed between Day 190 and pre-first treatment baseline (1st 6 months) and Day 358 versus Day 190 (2nd 6 months) using an ANCOVA model.

Possible covariates to be included into the model are SEQUENCE, MRC-MMT SCORE, CMT-TYPE and BASELINE where:

- SEQUENCE represents the treatment sequence from double blind to open-label (ACE-083 → ACE-083 or Placebo → ACE-083)
- MRC-MMT SCORE represents the conversion of the screening MRC-MMT grade to the decimal version as follows: 5 = 5.0, 5- = 4.67, 4+ = 4.33, 4 = 4.0, 4- = 3.67, 3+ = 3.33, 3 = 3.0, 3- = 2.67, 2+ = 2.33, 2 = 2.0, 2- = 1.67, 1+ = 1.33, 1 = 1.0
- CMT-TYPE refers to the type of CMT (e.g. CMT1 or CMTX)
- BASELINE represents the baseline value from the double-blind phase

Least squares estimates of the SEQUENCE effect and 90% confidence intervals will be provided.

### 10-Meter Walk/Run Test

The effect of ACE-083 administered during the open-label extension compared to the treatment administered in the double-blind placebo-controlled phase will be examined for those receiving ACE-083 during the double-blind phase and separately for those receiving placebo during the double-blind phase by comparing the absolute and/or percent changes observed between Day 190 and pre-first treatment baseline (1st 6 months) and Day 358 versus Day 190 (2nd 6 months) using an ANCOVA model.

Covariates to be included into the model are SEQUENCE, HEIGHT, CMT-TYPE, and BASELINE where:

- SEQUENCE represents the treatment sequence from double blind to open-label (ACE-083 → ACE-083 or Placebo → ACE-083)
- HEIGHT represents the height of the patient (cm)
- CMT-TYPE refers to the type of CMT (e.g. CMT1 or CMTX)
- BASELINE represents the baseline value of the parameter of interest from the double-blind phase

Least squares estimates of the SEQUENCE effect and 90% confidence intervals will be provided.

If the Day 358 and/or Day 190 assessments have no missing data, then the above ANCOVA model will be used for analysis. If missing data is present, a standard multiple imputation with the above ANCOVA model will be used for analysis as described in [Section 4.11.1](#).

In addition, a line graph of the mean ± SEM of the percent change from baseline will be provided by sequence for each scheduled time.

Additional analyses may be performed as appropriate.

### 6-Minute Walk Test

The effect of ACE-083 administered during the open-label extension compared to the treatment administered in the double-blind placebo-controlled phase will be examined for those receiving ACE-083 during the double-blind phase and separately for those receiving placebo during the double-blind phase by comparing the absolute and/or percent changes observed between Day 190 and pre-first treatment baseline (1st 6 months) and Day 358 versus Day 190 (2nd 6 months) using an ANCOVA model.

Covariates to be included into the model are SEQUENCE, HEIGHT, CMT-TYPE, and BASELINE where:

- SEQUENCE represents the treatment sequence from double blind to open-label (ACE-083 → ACE-083 or Placebo → ACE-083)
- HEIGHT represents the height of the patient (cm)
- CMT-TYPE refers to the type of CMT (e.g. CMT1 or CMTX)
- BASELINE represents the baseline value of the parameter of interest from the double-blind phase

Least squares estimates of the SEQUENCE effect and 90% confidence intervals will be provided.

If the Day 358 and/or Day 190 assessments have no missing data, then the above ANCOVA model will be used for analysis. If missing data is present, a standard multiple imputation with the above ANCOVA model will be used for analysis as described in [Section 4.11.1](#).

In addition, a line graph of the mean  $\pm$  SEM of the percent change from baseline will be provided by sequence for each scheduled time.

Additional analyses may be performed as appropriate

### **Berg Balance Scale**

The effect of ACE-083 administered during the open-label extension compared to the treatment administered in the double-blind placebo-controlled phase will be examined for those receiving ACE-083 during the double-blind phase and separately for those receiving placebo during the double-blind phase by comparing the absolute changes observed between Day 190 and pre-first treatment baseline (1st 6 months) and Day 358 versus Day 190 (2nd 6 months) using an ANCOVA model.

Covariates to be included into the model are SEQUENCE, CMT-TYPE, and BASELINE where:

- SEQUENCE represents the treatment sequence from double blind to open-label (ACE-083  $\rightarrow$  ACE-083 or Placebo  $\rightarrow$  ACE-083)
- CMT-TYPE refers to the type of CMT (e.g. CMT1 or CMTX)
- BASELINE represents the baseline value of the parameter of interest from the double-blind phase

Least squares estimates of the SEQUENCE effect and 90% confidence intervals will be provided.

If the Day 358 and/or Day 190 assessments have no missing data, then the above ANCOVA model will be used for analysis. If missing data is present, a standard multiple imputation with the above ANCOVA model will be used for analysis as described in [Section 4.11.1](#).

The statistical analysis described above will be done on the Per Protocol Set and will be considered primary. The analyses described above will also be repeated for the Full Analysis Set.

In addition, a line graph of the mean  $\pm$  SEM of the absolute change from baseline will be provided by sequence for each scheduled time.

Additional analyses may be performed as appropriate

### **Falls**

The hazard ratio of recurring falls between ACE-083 and placebo during the entire 12 months (excluding the screening interval) will be estimated using the Andersen-Gill recurrent events model with the following covariates: SEQUENCE, CMT-TYPE, PERIOD, and ankle dorsiflexion MRC-MMT decimal score where SEQUENCE refers to the treatment sequence from double-blind to open-label (ACE-083  $\rightarrow$  ACE-083 or Placebo  $\rightarrow$  ACE-083), and PERIOD

refers to the period of time of observation (“Double-blind”, “Open-label”). The “Double-Blind” period covers Weeks 1 to 24 and the “Open-label” period covers Weeks 25 to 48. The point estimate, p-value and 90% confidence interval for the hazard ratio for SEQUENCE will be provided.

Additional methods for the statistical analysis of the recurring event of falls may be considered and performed as appropriate (e.g. negative binomial regression with similar covariates as listed for the Andersen-Gill recurrent events model described above).

No multiple imputations will be performed for missing data.

The statistical analyses described above will be done on the Per Protocol Set and will be considered primary. The analyses described above will also be repeated for the Full Analysis Set.

Additional analyses may be performed as appropriate.

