### **Falls**

Individual data on the number and type of falls recorded in 4-week time intervals along with details on the timing and classification of the individual falls recorded, type of assistance, and information related to input (whether the fall was recorded by device detection or recorded by the individual patient) will be provided in a listing.

The number of falls, as well as the number of patients who fell at least once occurring from Week 1 to Week 24 (6 months) will be summarized by treatment group. Summaries will be provided for the additional subintervals between Weeks 1 and 24 as outlined in [Section 4.7.1.2](#). A record of “Near-fall” will not be counted as a “Fall”.

The hazard ratio of recurring falls between ACE-083 and placebo between Weeks 1 and 24 will be estimated using the Andersen-Gill recurrent events model with the following covariates: TREATMENT, CMT-TYPE, and ankle dorsiflexion MRC-MMT decimal score where the covariates are defined similarly as what was described for MVIC. The point estimate, p-value and 90% confidence interval for the hazard ratio for TREATMENT will be provided.

Additional methods for the statistical analysis of the recurring event of falls may be considered and performed as appropriate (e.g. negative binomial regression with similar covariates as listed for the Andersen-Gill recurrent events model described above).

No imputations will be performed for missing data.

The statistical analyses described above will be done on the Per Protocol Set and will be considered primary. The analyses described above will also be repeated for the Full Analysis Set.

Additional analyses may be performed as appropriate.

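### On total study time PERIOD adjusts for nothing in the 12-month falls model, so the single SEQUENCE hazard ratio, described as ACE-083 versus placebo, mixes placebo-controlled and all-active time

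*SAP*

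**What the plan says.** SAP section 4.7.2.2.3, Falls, gives its target as "The hazard ratio of recurring falls between ACE-083 and placebo during the entire 12 months", estimated with an Andersen-Gill model "with the following covariates: SEQUENCE, CMT-TYPE, PERIOD, and ankle dorsiflexion MRC-MMT decimal score". SEQUENCE is the treatment order: ACE-083 then ACE-083, or placebo then ACE-083. PERIOD "refers to the period of time of observation", and its levels are cut by study week: "The “Double-Blind” period covers Weeks 1 to 24 and the “Open-label” period covers Weeks 25 to 48". Only one contrast is to be reported: "The point estimate, p-value and 90% confidence interval for the hazard ratio for SEQUENCE will be provided". The paragraph lists no interaction and no time-varying treatment indicator, and it states neither the time axis nor the variance estimator. A count model is allowed as an optional extra: "negative binomial regression with similar covariates as listed for the Andersen-Gill recurrent events model described above".

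Four other places bear on the point:

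- SAP section 4.7.2.2.1, Falls, already plans the randomised comparison: "The hazard ratio of recurring falls between ACE-083 and placebo between Weeks 1 and 24 will be estimated using the Andersen-Gill recurrent events model". That model has TREATMENT and no PERIOD term.
- SAP section 3.2 puts every patient on ACE-083 in the extension.
- SAP section 4.1.5 identifies the Day 190 dose as the first open-label dose.
- SAP section 2.3 and protocol section 6 class falls as exploratory.

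**The concern.** A reader who sees PERIOD in the covariate list will assume that the model handles the move from placebo-controlled to all-active treatment. On the usual Andersen-Gill clock it does not. PERIOD depends on study time alone, and the unspecified baseline hazard already absorbs anything that depends on time alone. No other listed term lets the SEQUENCE effect differ between periods.

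What is at stake is the meaning of the one reported number. It carries an ACE-083 versus placebo description, but for about half the follow-up nobody is on placebo. If the drug reduces falls, this ratio will understate the reduction. It will also differ by construction from the Weeks 1 to 24 ratio, which carries the same description.

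**Working it through.** The documents give no fall rate, hazard ratio or power for falls, so there is no planned figure to reproduce. Step 1 is algebra. Steps 2 to 4 rest on assumed rates and effects and are illustrations.

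**Step 1. PERIOD on total study time.** For a fall by patient i at study time t, the partial-likelihood factor is

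exp(βx_i + γP(t)) / Σ_j exp(βx_j + γP(t)), summed over the patients j at risk at t.

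P(t) is the same for all of them, so exp(γP(t)) cancels. The score and information for γ are zero whatever the fall rates. I checked this on one simulated trial: 20 versus 20 patients, cut at Day 168, end at Day 336, 0.10 falls per patient-week on placebo, treatment hazard ratio 0.5, 103 falls.

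| Clock | PERIOD log HR | PERIOD information | SEQUENCE log HR |
|---|---|---|---|
| Total study time | not estimable | 0 | -0.588 |
| Reset at each period | -0.731 | 22.1 | -0.591 |
| Gap time | -0.727 | 21.3 | -0.573 |

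On total time the SEQUENCE log hazard ratio was -0.588389 with PERIOD in the model and -0.588389 without it. SEQUENCE×PERIOD, with no PERIOD main effect, was estimable in the same trial (1.446, SE 0.455).

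**Step 2. What the SEQUENCE ratio averages.** Let the placebo fall rate be λ, the true ratio h, the two periods equally long, and the effect immediate.

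- ACE-083 then ACE-083: hλ + hλ = 2hλ
- Placebo then ACE-083: λ + hλ = (1+h)λ
- Ratio: 2h/(1+h)

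For h = 0.5 this is 1.0/1.5 = 0.67. For h = 0.6 it is 1.2/1.6 = 0.75. For h = 0.7 it is 1.4/1.7 = 0.82.

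If the underlying rate in the second half is r times that in the first, the ratio becomes h(1+r)/(1+rh). With r = 0.7 this gives 0.85/1.35 = 0.63 for h = 0.5 and 1.19/1.49 = 0.80 for h = 0.7. The pull is weaker but still there.

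**Step 3. Simulation check.**

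| True h | 2h/(1+h) | 12-month SEQUENCE ratio | Double-blind ratio | Open-label ratio |
|---|---|---|---|---|
| 0.5 | 0.67 | 0.65 | 0.48 (Weeks 1 to 24 model) | not run |
| 0.7 | 0.82 | 0.83 | 0.71 (Weeks 1 to 24 model) | not run |
| 0.6 | 0.75 | 0.75 | 0.59 (SEQUENCE×PERIOD) | 1.02 (SEQUENCE×PERIOD) |

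Rows 1 and 2 use 150 runs each, 0.10 falls per patient-week on placebo, no frailty and about 10% early exit. Row 3 uses 200 runs, 4 falls per 48 weeks on placebo and gamma frailty variance 0.7; its 0.75 is a geometric mean. The interaction model recovers the simulated truths of 0.6 and 1.0 closely.

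**Step 4. The period cut.** Week w starts on Day 7(w-1)+1. Week 25 therefore starts on Day 7×24+1 = 169, which is the day of the ninth and last blinded dose. Day 190 is 7×27+1, the start of Week 28. Days 169 to 189 are 21 days, so three blinded weeks are labelled open-label.

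- With 27 blinded and 21 open-label weeks, the 48-week ratio is 48h/(27+21h): 24/37.5 = 0.64 for h = 0.5 and 33.6/41.7 = 0.81 for h = 0.7.
- The ratio for the 24 weeks labelled open-label is 24h/(3+21h): 12/13.5 = 0.89 for h = 0.5 and 16.8/17.7 = 0.95 for h = 0.7. Under these assumptions a clean open-label period would give 1.

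**The case against.** The other side has several fair points.

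- **The paragraph never asks for a PERIOD estimate.** From the section title, a reader might infer that the plan has lost its open-label versus double-blind contrast for falls and that this contrast cannot be obtained. The documents do not support that. Most neighbouring endpoints include a sentence comparing the first and second six months within each arm; the falls paragraph does not, and it reports only SEQUENCE. Sections 4.7.2.2.1 and 4.7.2.2.2 also summarise falls and fallers by treatment for Weeks 1 to 24 and 25 to 48. The optional count model could estimate PERIOD.
- **The redundant term does no harm.** This stands: the SEQUENCE estimate is the same with and without it. The mixing would also be there if PERIOD had never been listed. The defect is the absent interaction together with the description of the result.
- **The clock is not stated.** This stands too. With a reset at each period, or on gap time, PERIOD can be estimated. Section 4.7.1.2 defines the 12-month variable from Week 1 to Week 48, which fits total time but does not settle it. The choice does not cure the mixing: the SEQUENCE log hazard ratio was between -0.573 and -0.591 on all three clocks.
- **An undiluted randomised result exists elsewhere.** The Weeks 1 to 24 model supplies it, which limits the damage.
- **The 48-week SEQUENCE ratio is a legitimate comparison of early with delayed start.** Agreed, but the SAP does not describe it that way.

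The optional negative binomial model is not a full answer. With similar covariates it would carry the same main effects and again force one SEQUENCE ratio across both periods.

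**Conclusion.** The point holds in a limited form. On total study time the PERIOD main effect carries no information and separates nothing; that part is exact but conditional on the clock. The consequence is one 48-week ratio described as ACE-083 versus placebo that averages active-versus-placebo with active-versus-active time. Its size is illustrative: a true ratio of 0.5 would appear as about 0.67 and 0.7 as about 0.82, assuming similar underlying rates, equal periods and an immediate effect. The direction does not depend on the exact rates, provided that the drug acts similarly in both sequences once given.

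It would go too far to say that the model cannot be fitted, that the SEQUENCE estimate is corrupted by PERIOD, or that a promised falls result is lost. Falls are exploratory and the randomised Weeks 1 to 24 analysis is unaffected by the mixing, so the priority is modest.

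**What to change.** In SAP section 4.7.2.2.3, Falls:

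1. State that the Andersen-Gill model runs on total study time.
2. Replace the PERIOD main effect with SEQUENCE×PERIOD, keeping SEQUENCE, CMT-TYPE and the MRC-MMT score, and use patient-clustered robust variance.
3. Report the SEQUENCE hazard ratio with its 90% interval separately for each period. Describe only the double-blind ratio as ACE-083 versus placebo.
4. If an open-label versus double-blind contrast within each sequence is wanted, add a count model, not necessarily as primary. Use one record per patient and period, a log(weeks observed) offset, SEQUENCE, PERIOD, SEQUENCE×PERIOD, and a within-patient correlation term. State that this contrast is confounded with time on study and with unblinding.
5. Reconcile the Week 25 (Day 169) cut with the Day 190 start of open-label dosing given in section 4.1.5.

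The cost is SAP wording and minor programming, with no new data. The period-specific intervals will be wider than a single 48-week interval.

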## Part 2 (Open-label Extension)

For assessments performed in the open-label extension the baseline is defined to be the Day 190 assessment.

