### 4.1.5. Data Handling Conventions

Unless otherwise stated or indicated:

- Individual data for all patients will be presented in data listings, sorted by “Study Part” (Part 1 or Part 2), “Treatment Group”, and “Patient Number”;
- For any parameter analyzed, only observations from visits and/or time points planned in the protocol will be used in descriptive statistics. An exception to this rule is for a baseline assessment. Should an unscheduled assessment be taken after the scheduled baseline assessment but before the first dose of study medication, then the unscheduled assessment may be used as the baseline;
- For variables where the Day 1 assessment is defined as the baseline, should an individual patient have a Day 1 assessment after having received their first dose, then an unscheduled assessment may be used as the baseline, provided that the unscheduled assessment was done prior to first dose.
- Should a patient be assigned to the wrong CMT-type stratum (e.g. a CMT1 patient assigned to the CMTX stratum or a CMTX patient assigned to the CMT1 stratum), the patient’s true CMT-type (CMT1 or CMTX) will be used in statistical models where CMT-type is used as a covariate.
- With the exception of what is described in the preceding bullet, unscheduled assessments will not be collectively summarized in summary tables or figures; however, these data will appear in individual patient listings.
- For adverse events where the assessment of “Relationship to study drug” is missing, it will be assumed that the adverse event is “Probably Related” to study drug.
- For selected pharmacodynamic and efficacy data, tests of statistical hypotheses and estimation using the end-of-treatment visit or the Day 190 visit (Part 2 double-blind component), multiple imputation for missing data will be performed. Additional techniques for handling missing data may also be considered and evaluated.
- If a patient has a Day 190 assessment performed after having received the Day 190 dose (first dose in the open-label phase), then the Day 190 assessment for that patient will be included in statistical analyses of Day 190 data only if the difference between the Day 190 assessment and the Day 190 dose date is less than or equal to 7 days.
- Descriptive statistics for quantitative parameters will be provided using number of observations (N), mean, standard deviation (SD), standard error of the mean (SEM), median, minimum and maximum;

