- Should it be necessary to convert duration in days to duration in months, the duration in days will be divided by 30.417 (365/12) to calculate duration in months.

- Descriptive statistics for qualitative parameters will be provided using frequencies (N) and percentages (%).
- If the result of a continuous variable contains nonnumeric values (e.g. ‘<X’ or ‘>X’), the imputed values used for the descriptive statistics will be determined by considering the following rules:
  - If the value is ‘<X’, the value used will be X/2;
  - If the value is ‘>X’, the value used will be X.
- Concerning the determination of absolute and percent change from baseline for data such as MRI and muscle strength where assessments are reported separately for the left and right sides and the average absolute and/or percent change from baseline is needed, the absolute and/or percent change is determined for the left and right sides separately and then averaged. The “average” represents the “average” absolute (or percent) change from baseline for the left and right sides. For MRI and muscle strength data, should a patient have an MRI and/or strength assessment on one side (i.e. right side) but not the other side at an individual time point, the value for the average absolute (or percent) change from baseline for that patient and time point will be the absolute (or percent) change from the side from which the MRI and/or strength assessment was obtained.

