### **Falls**

Individual data on the number and type of falls recorded in 4-week time intervals along with details on the timing and classification of the individual falls recorded, per day, type of assistance, and information related to input (whether the fall was recorded by device detection or recorded by the individual patient) will be provided in a listing. This data will be included with the data collected in the double-blind placebo-controlled phase.

The number of falls as well as the number of patients who fell at least once occurring from Week 25 up to Week 48 inclusive will be summarized by treatment, including separate summaries for subintervals as outlined in [Section 4.7.1.2](#). A record of “Near-fall” will not be counted as a “Fall”.

Additional analyses may be performed as appropriate.

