### Representation of Scheduled Times in Listings

Because data for this study comes from multiple sources, such information will be standardized in the listings.

The standardization is outlined below:

Lab (MRL), CMT-HI, eCRF (long)	eCRF (short)	MRI	Mapping for Tables and Listings	Plots
Screening Day -28 to Day -7	SCN		S1D-28	-28
Dose 1 Day 1	DOSE1D1	DAY 1	D1D1	1
Dose 1 Day 2	DOSE1D2		D1D2	2
Dose 1 Day 8	DOSE1D8		D1D8	8
Dose 2 Day 22	DOSE2D22		D2D22	22
Dose 3 Day 43	DOSE3D43	DAY 43	D3D43	43
Dose 4 Day 64	DOSE4D64		D4D64	64
Dose 5 Day 85	DOSE5D85		D5D85	85
Follow-Up Day 106/ET a	ET	DAY 106	F1D106_ET	106
Dose 6 Day 106 b	DOSE6D106	DAY 106	D6D106	106
Dose 7 Day 127 b	DOSE7D127		D7D127	127
Follow-Up Day 141 a	FUP	DAY 141	F2D141	141
Dose 8 Day 148 b	DOSE8D148		D8D148	148
Dose 9 Day 169 b	DOSE9D169		D9D169	169
Dose 10 Day 190 b	DOSE10D190	DAY 190	D10D190	190
Dose 11 Day 211 b	DOSE11D211		D11D211	211
Dose 12 Day 232 b	DOSE12D232		D12D232	232
Dose 13 Day 253 b	DOSE13D253		D13D253	253
Dose 14 Day 274 b	DOSE14D274		D14D274	274

Lab (MRL), CMT-HI, eCRF (long)	eCRF (short)	MRI	Mapping for Tables and Listings	Plots
Dose 15 Day 295 b	DOSE15D295	DAY 295	D15D295	295
Dose 16 Day 316 b	DOSE16D316		D16D316	316
Dose 17 Day 337 b	DOSE17D337		D17D337	337
Day 358/ET b	ET	DAY 358	F1D358_ET	358
Follow-Up Day 393 b	FUP	DAY 393	F2D393	393

a Applies to Part 1; b Applies to Part 2

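### The falls analyses label Weeks 25 to 48 as open-label, but on the planned schedule Weeks 25 to 27 are still blinded (minor; exploratory endpoint)

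*SAP*

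**What the plan says.** Falls are cut by study week. SAP 4.7.1.2 (Falls) defines intervals ending at Weeks 24 and 48 and labels these 6 and 12 months. Three analyses use them:

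- Double-blind (SAP 4.7.2.2.1, Falls): "The hazard ratio of recurring falls between ACE-083 and placebo between Weeks 1 and 24 will be estimated" with an Andersen-Gill model.
- Open-label (SAP 4.7.2.2.2, Falls): fall counts and patients with at least one fall "occurring from Week 25 up to Week 48 inclusive will be summarized by treatment".
- Twelve-month model (SAP 4.7.2.2.3, Falls): a PERIOD covariate in which double-blind is Weeks 1 to 24 and the open-label "period covers Weeks 25 to 48".

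Elsewhere the boundary is Day 190. The visit map in SAP Section 6 shows "Dose 10 Day 190", with Dose 9 on Day 169. SAP 4.1.5 refers to "the Day 190 dose (first dose in the open-label phase". SAP 4.1.4 states: "For assessments performed in the open-label extension the baseline is defined to be the Day 190 assessment". SAP 4.3 counts the double-blind period as completed once the Day 190 visit is done.

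**The concern.** If Week 24 ends before the first open-label dose, the falls analyses and the dosing schedule disagree about when blinded treatment stops. The weeks in between are then missing from the randomized comparison and are counted under the open-label label. For patients randomized to placebo, falls that occurred before any ACE-083 would be reported as falls during ACE-083 treatment. SAP 4.1.3 also allows an open-label column pooled over sequences and headed only with the drug name; if the falls summary uses it, the same placebo time would appear there.

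**Working it through.** **Inputs.** Dose 9 on Day 169, Dose 10 on Day 190 and Dose 17 on Day 337 (SAP Section 6); the falls windows (SAP 4.7.1.2 and 4.7.2.2.1 to 4.7.2.2.3); the exposure formula (SAP 4.6.1). The SAP does not define week numbering. Week 1 is taken to start on Day 1, in line with the 12-month model leaving out the screening interval.

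**Weeks.** Week of Day d = floor((d − 1)/7) + 1.

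- Week 24 ends on Day 24 × 7 = 168.
- Day 169 (Dose 9): 168/7 + 1 = Week 25, first day.
- Week 27 ends on Day 27 × 7 = 189.
- Day 190 (Dose 10): 189/7 + 1 = Week 28, first day.

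Weeks 25 to 27 are therefore exactly the 21 days that follow the last blinded dose. Counting elapsed weeks, (d − 1)/7, puts Days 169 and 190 at 24.0 and 27.0, which leads to the same conclusion. Starting the clock at screening would move Week 24 earlier still.

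**The SAP's own exposure formula.** Exposure in weeks is (last dose date − first dose date + 21)/7. Double-blind: (169 − 1 + 21)/7 = 27. Open-label: (337 − 190 + 21)/7 = 24. The plan's figures thus give 27 + 24 weeks, not 24 + 24.

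**The month labels.** SAP 4.1.5 says "the duration in days will be divided by 30.417 (365/12) to calculate duration in months". On that rule 168 days are 168/30.417 = 5.5 months and 189 days are 6.2 months, so calling Week 24 six months does not rescue the cut.

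**Open-label summary.** 21/168 = 12.5% of the window is blinded time. Let RR be the assumed on-drug fall-rate ratio against placebo.

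- Immediate full effect: overstatement = (3 + 21·RR)/(24·RR) − 1, which is 1.4% for RR 0.90, 5.4% for 0.70 and 12.5% for 0.50.
- Effect building evenly over 12 weeks, compared with Weeks 28 to 48: the on-drug total over 21 weeks is T = 12·(1 + RR)/2 + 9·RR, and the overstatement is [(3 + T)/24]/[T/21] − 1. T is 19.5, 16.5 and 13.5, giving 1.0%, 3.4% and 6.9%. For RR 0.50: (16.5/24)/(13.5/21) = 0.6875/0.643 = 1.069.
- In a column pooled over two equal sequences, the immediate-effect figures halve to about 0.7%, 2.7% and 6.2%.

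**Double-blind hazard ratio.** 21/189 = 11.1% of planned blinded time is left out. With a constant Poisson rate the standard error ratio is sqrt(27/24) = 1.061. With overdispersion k and mean m falls per 12 weeks it is sqrt[(1/(2m) + k)/(1/(2.25m) + k)]. For assumed m from 1 to 4 and k from 0.5 to 1 this runs from 1.006 to 1.029.

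**Visit windows.** Protocol Appendix 1, Table 6 sets windows relative to the previous dose: ±1 day at Day 22, then eight of ±3 days. The first open-label dose can therefore fall between Day 1 + 20 + 8 × 18 = 165 and Day 1 + 22 + 8 × 24 = 215. Footnote 22 of the same table allows ±3 days for every dose, which would give Day 163 to Day 217; the two should be reconciled.

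**The case against.** The strongest reply is that Weeks 1 to 24 is a deliberate fixed window. It is common to both arms, keeps nearly all open-label exposure out without censoring patient by patient, and matches the 4-week intervals in which falls are listed (Weeks 24 and 48 are 6 and 12 such blocks). For the double-blind hazard ratio this stands: the window is a valid choice that costs a little precision. It does not justify calling Weeks 25 to 27 open-label. Nor does the 4-week listing force the cut, because the same listing comes "along with details on the timing and classification of the individual falls recorded".

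Four stronger readings are tempting, and the documents do not support them.

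- A reader might infer that the double-blind comparison is biased. It is not: both arms are cut at the same week.
- A reader might infer that the 12-month SEQUENCE hazard ratio is distorted. On a time-since-first-dose scale, a PERIOD cut at a fixed week is constant within every risk set, so moving the cut does not change that ratio. The SAP does not state the time scale.
- A reader might infer that every patient is blinded through Week 27. That holds for the planned schedule. If visits scatter evenly within their windows (assumed), about 47% of patients would start open-label before Day 190.
- A reader might infer an undeclared departure from the protocol. Protocol 14.2.3 splits changes in assessments at Day 190, but falls are counts, and the protocol sets no explicit cut for them.

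**Conclusion.** The label is wrong as written, and the correction is minor. Following the SAP on the planned schedule puts three weeks of blinded time into the open-label falls summary. The clear consequence is in the placebo-to-ACE-083 sequence, where 12.5% of the window is placebo time. The overstatement there is about 1% to 12.5%, depending on the assumed drug effect and its onset; the documents give no fall rates to narrow this. The double-blind hazard ratio loses some precision and nothing else. The protocol lists falls among the exploratory endpoints, so no primary or secondary conclusion depends on this.

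**What to change.** - **Open-label summary (SAP 4.7.2.2.2) and the matching definitions in 4.7.1.2.** Start open-label falls time at each patient's first open-label dose, including when that is before Day 190, so that early starters' days are not lost. Run it to a stated end, for example 24 weeks later or the Day 358/ET visit. The present Week 48 limit is Day 336, one day before planned Dose 17.
- **Double-blind analysis (SAP 4.7.2.2.1).** Extend the time at risk to the day before the first open-label dose, capped at Day 189 (end of Week 27).
- **Twelve-month model (SAP 4.7.2.2.3).** Keep PERIOD as a fixed-week label and cut it after Week 27.
- **Reporting.** Give falls as rates per patient-week. For the proportion with at least one fall, state a common window and how open-label days of early starters are handled.

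The cost is SAP wording and date logic; no new data are needed. There are three downsides. The periods have unequal length. The cuts no longer follow the 4-week listing intervals. For late starters, blinded days after Day 189 are in neither summary: at most 25 days under the column windows (Days 190 to 214), or 27 under footnote 22.

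Two separate small corrections belong in the same revision. The open-label subintervals in SAP 4.7.1.2 stop at Week 40 and should cover the whole period. The percent-change falls criterion in SAP 4.7.2.3 is undefined for a patient with no falls in Weeks 1 to 12, so it should be replaced, for example by an absolute change in fall rate, or dropped.
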